6.2 The rationale for choices of method/s (tied to project aims/objectives)

There is a large evidence-base to support the LISTEN program: 1) Problem-Solving Therapy (PST), has been shown to be effective in reducing distress, depression, and anxiety in a variety of settings and patient populations (including adults with diabetes and CVD), 2) our previous pilot work (*DUHREC Project reference: 2020-297*) provides preliminary data to support the feasibility and acceptability of training AHPs to deliver LISTEN via telehealth.

This design promotes examination of both (cost) effectiveness and implementation outcomes, rapidly moving knowledge from research to implementation.(49)

7. The participants including:

7.1 A description and the number of participants

Allied Health professionals: 4 to 10 (plus two 'back-ups')

People with diabetes: Up to 40 'volunteer training cases' (max 4 assigned per AHP) (Objective 2), 454-604 trial participants (Objective 3) and a subsample of the trial participants (n=20-30; Objective 5).

Key stakeholders from partner organisations: 5-16 AHPs who deliver LISTEN, project leads and decision makers (Objective 5)

7.2 The inclusion and exclusion criteria

To be eligible to participate, AHP participants must meet the following criteria:

- qualified allied health professional experienced in providing diabetes treatment and/or education to adults with diabetes (a minimum of 12 months working in a diabetes setting)
- previous training or experience in supporting people with emotional problems
- willingness and availability to undertake the training and deliver the LISTEN program

To be eligible to participate as a training case (Objective 2) or participate in the effectiveness trial (Objective 3) people with diabetes must meet the following criteria.

- living in Australia
- aged 18 years or older
- have a diagnosis of diabetes (with or without CVD)
- have a total score of 25 or greater on the Problem Areas In Diabetes (PAID) scale, indicating at least mild diabetes distress
- have a score less than 6 on the four-item Patient Health Questionnaire (50) (PHQ-4; a score greater than or equal to 6 indicates moderate-severe symptoms and warrants further assessment and follow-up)

The following pathways for people with diabetes will be applied depending on their scores:

Table 1: Eligibility criteria for the RCT (Objective 3) in terms of mental health screening

Participants' sco	re on:	Criteria	Eligible
PAID (0-100)	PHQ-4	Cineria	
Total <25	<6	No/minor diabetes distress and no/mild general symptoms	Noa
Total <25; and \geq 2 on \geq 3 items#	<6	Mild diabetes distress and no/mild general symptoms	Yes
Total 25-75	<6	Moderate-to-severe diabetes distress but no/mild general symptoms	Yes
Total >75	<6	Severe diabetes distress but no/mild depressive or anxiety symptoms	Yes
Total >75	>6	Severe diabetes distress plus at least moderate depressive or anxiety symptoms	Nob

[#] Score of ≥ 2 on a PAID item = at least moderate problem;

To be eligible to participate in the semi-structured interviews (Objective 5), stakeholders from the partner organisations must be an AHP who is a consenting participant in the project, or is a staff member employed at one of the partner organisations who is involved in the service delivery of the LISTEN intervention.

7.4 Your participant recruitment strategies and timeframes (as required in addition to that outlined in the HREA)

Allied Health professionals: will be recruited via newly appointed and existing AHPs who provide 'on-call' services via Diabetes Australia. Diabetes Australia will oversee the recruitment of newly appointed and existing AHPs during the first two months of the project. Recruitment adverts will clearly describe what is involved in the project, the expectations from the position and time commitment. Interested AHPs can apply for the position directly through our partners who will be responsible for advertising the positions. The volunteer AHPs will be provided with a Plain Language Statement (Appendix 1) and their informed consent will be required before they can participate in the project. Existing AHPs who provide 'on-call' services via the NDSS Helpline will be provided up to two weeks to consider participation. Diabetes Australia will commit four to 10 diabetes AHPs to participate in the project and two additional diabetes AHP to participate in the workshop only.

People with diabetes:

1) 'Training cases' (Objective 2). Recruitment of target sample (N=<40) is planned for a 2-month period.

Participants who consent to being volunteer 'training cases' (**Appendix 2**) will be recruited via the NDSS Registry, of whom, approximately 1.4 million people are registered. The NDSS will send out invitations, via e-mail, directly to registrants who have consented to be contacted about research. The research team will not have access to potential participant's details unless they contact us regarding the study, or they enrol into the study.

The final number of people with diabetes recruited to volunteer for 'training cases' will be determined by the AHPs' ability to deliver LISTEN as intended (as determined by the PST-PAC fidelity measure – see **Section 8.1** and **Appendix 14**).

Volunteer 'training cases' (adults with diabetes who) are interested in participating will be directed to an online (Qualtrics) survey. The Qualtrics survey will begin with a PLS and consent form (**Appendix 2**). Following provision of informed consent, participants will be asked to complete eligibility questions online. Eligibility will be automatically determined based on responses and ineligible participants will be thanked for their interest in the study. Eligible participants will be

^{a.} Offered referral to NDSS factsheets about emotional health;

b. Provided with resources / referral to MH services and/or a referral to their GP

directed to complete an online baseline survey to collect demographic and clinical information about the participant (**Appendix 8**).

Volunteer 'training cases' (participating adults with diabetes) will be e-mailed a \$50 e-Gift card on completion of the study (i.e. complete pre-post online surveys and a minimum of one LISTEN session) as a token of appreciation and to aid recruitment.

2) Effectiveness trial (Objective 3) and cost-effectiveness (Objective 4). Recruitment of target sample (N=454-604) is planned for a 6-month period.

The primary method of recruitment will be a national e-mail using the NDSS Registry. The NDSS will send out invitations directly to potential participants. The research team will not have access to potential participant's details unless they contact us regarding the study, or they enrol into the study. Our prior experience using the NDSS database for recruitment purposes indicates a response rate of approximately 15%. Thus, to recruit a sample of up to N=454 participants, study invitations, and 2- week follow-up reminders, must be sent to a random sample of at least N=2,600 NDSS registrants. E-mail invitations will be staggered over the 6-month recruitment period.

In addition, the study will be advertised on the ACBRD website, e-newsletter/blogs and social media (Twitter, Facebook) via the researchers' affiliated professional accounts (e.g. Deakin University, ACBRD; see **Appendix 16** for Recruitment Flyer). Australian diabetes charities, organisations and associations (e.g. Diabetes Australia, Diabetes Victoria and other state diabetes organisations) will be notified of, and encouraged to promote, the study through similar online means including the research section on their websites, e- newsletters sent to people with type 2 diabetes (e.g. 'Loop', 'Membership Maters'), as well as their Facebook and twitter accounts. Investigators and colleagues will be asked to consider circulating the study flyer (**Appendix 16**) amongst their networks.

People with diabetes who are interested in participating will be directed to an online (Qualtrics) survey. The Qualtrics survey will begin with a PLS and consent form (**Appendix 3**). Following provision of informed consent, participants will be asked to complete eligibility questions online. Eligibility will be automatically determined based on responses and ineligible participants will be thanked for their interest in the study. Eligible participants will be directed to complete an online baseline survey to collect demographic and clinical information about the participant (**Appendix 9**).

Those who are not eligible (as determined through the screening survey) will be provided with links to the NDSS emotional health and diabetes factsheets (practical, evidence-based resources about recognising and addressing emotional health problems and resources for support). In addition to receiving links to mental health fact sheets, those not eligible for the project because of indications of 'severe diabetes distress and moderate-severe symptoms of depression or anxiety' (see **Section 7.2**) will be provided with links to mental health support services (e.g. Beyond Blue) and recommended to speak with their primary care provider (e.g. general practitioner).

Participating adults with diabetes will be e-mailed a \$30 e-Gift card on completion of the study (i.e. complete baseline, 8-week and 6-month follow-up online surveys) as a token of appreciation and to aid recruitment.

- 3) Exploring barriers and enablers to Reach, Adoption and Implementation (Objective 5).
- Recruitment of 5-16 stakeholders from partner organisations will include AHPs enrolled in the study as well as key staff from partner organisations who are involved in service delivery.
- A random sample of participants assigned to the intervention group will be invited to take part. We will continue to recruit intervention participants until the target sample (minimum 20) is reached.

Recruitment will commence in year 2 of the project.

Participating adults with diabetes in the intervention group who are randomly selected to take part in the semi-structured interviews will be e-mailed a \$25 e-Gift card on completion of the study (i.e. complete phone/zoom/skype interview) as a token of appreciation and to aid recruitment.

7.5 Your approach/es to provision of information to participants and/or consent (as required in addition to that outlined in the HREA)

Allied Health professionals: Participating AHPs will be newly employed staff who apply to undertake this role, or existing AHPs employed by Diabetes Australia who actively express an interest and desire in taking part in the study. They will be aware of the study requirements and expectations of their involvement before agreeing to take on the role and consenting to take part in the study. The research team will direct AHPs to an online PLSCF (**Appendix 1**). The PLSCF will describe the purpose of the study, the procedures to be followed, the risks and benefits of participation and contact details (email address and telephone number) for the research team in the event of any queries or questions. Prior to completing any study component, AHPs will need to tick a box to confirm they have read and understood the PLS and consent to taking part. Consent will be voluntary and free from coercion. AHPs will be encouraged to print a copy of the PLSCF for their records.

People with diabetes: All recruitment advertisements for volunteer 'training cases' (adults with diabetes; Objective 2) and participants with diabetes (effectiveness trial; Objective 3) will have a link directing people to an online Qualtrics survey. The Qualtrics survey will begin with the PLSCF (Appendix 2 and Appendix 3). Participants will have the option to download the PLSCF if preferred and will also be able to request for a hard copy of the forms to be posted to them. Participants will need to have read the PLSCF and have agreed to take part in the project (through the online consent form) before they can proceed to the eligibility screening and baseline survey. As described in Section 7.4, people will be informed of their eligibility to take part in the project on completion of the eligibility screening survey.

Stakeholders: AHPs and participants allocated to the intervention group will be asked to provide consent to take part in the semi-structured interviews (**Appendix** 2: AHPs and **Appendix 3:** participant with diabetes). Staff involved in service delivery will be required to read and sign an electronic consent form (Appendix 5: Stakeholders) prior to taking part in the interviews.

7.6 If necessary, the type of consent provided to different participant groups, when and where, and any arrangements to confirm that consent

Allied Health Professionals: The PLSCF will be made available to the AHPs via an online Qualtrics link (Appendix 1). The PLSCF will describe the study's purpose and procedures, the risks and benefits of participation and contact details (email address and telephone number) for the research team in the event of any queries or questions. Prior to completing any study component (i.e. responding to initial survey), potential participants will need to tick a box to confirm they have read and understood the PLS and consent to taking part. The researchers will then follow up with the participating AHPs by phone to verbally confirm their consent before arranging training dates.

People with diabetes: All advertisements relating to the project will have a link that directs people to a Qualtrics-hosted online PLSCF (**Appendix** 2: AHPs and **Appendix 3:** participant with diabetes). An online PLSCF will be developed and will describe the purpose of the study to participants, the procedures to be followed, the risks and benefits of participation and contact details (email address and telephone number) for the research team in the event of any queries or questions. Prior to completing any study component (i.e. responding to screening questions to determine eligibility), potential participants will need to tick a box to confirm they have read and understood the PLS and consent to taking part. Consent will be voluntary and free from coercion. Participants will be encouraged to print a copy of the PLSCF for their records. The consent procedure will be online.

Stakeholders: Stakeholders from the partner organisations will be e-mailed an electronic copy of the PLSCF. Prior to taking part in the interview, they are required to sign and return the PLSCF confirming that they have read and understood the information and consent to taking part in the project.

Participating AHPs, people with diabetes and stakeholders from the partner organisations will be informed that they can withdraw their consent at any time by contacting the research team or completing the 'Withdrawal Form'.

7.7 If necessary, details of who will be confirming or re-negotiating consent with participants and the process/es that will be undertaken

Not applicable

8. Research Activities:

What you are going to do? Please include:

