Consent and screening for eligibility: People with diabetes who are interested in participating will be directed to a Qualtrics page containing a plain language statement and consent form (PLSCF). An online PLSCF will describe the purpose of the study to participants, the procedures to be followed, the risks and benefits of participation and contact details (email address and telephone number) for the research team in the event of any queries or questions. Prior to completing any study component (i.e. responding to screening questions to determine eligibility), potential participants will need to tick a box to confirm they have read and understood the PLS and consent to taking part. Participants will also be asked to sign a Services Australia consent form to access their Medicare Benefits Schedule (MBS) and/or Pharmaceutical Benefits Scheme (PBS) data. Signing this consent form is voluntary. If they decide not to sign the MBS/PBS consent form it will not affect their participation in the LISTEN Study and they will still be eligible to take part.

Following provision of informed consent, participants will be asked to complete eligibility screening questions (**Appendix 9**; see Section 7.2 for eligibility criteria and Section 13 for a summary of the screening questions). Eligibility will be automatically determined based on responses to the questions. Those who are not eligible (as determined through the screening survey) will immediately be notified and provided with links to the NDSS emotional health factsheets (practical, evidence-based resources about recognising and addressing emotional health problems: https://www.ndss.com.au/living-with-diabetes/health-management/mental-health/). Those not eligible for the project because of indications of 'severe diabetes-distress and moderate-severe symptoms of depression or anxiety' (see Section 7.2) will also be provided with links to external mental health support (e.g. Beyond Blue) and a recommendation to speak with their primary health care provider (e.g., general practitioner). The contact details for a member of the research team will be provided on the Qualtrics form should the individual wish to discuss support available.

Randomisation: Eligible participants will be directed to complete an online (pre-intervention) baseline survey. Following baseline assessment, eligible participants will be randomised to

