13.1 Please describe your outcome measures

Objective 2: LISTEN Allied Health Professional Training

AHP competency and fidelity will be assessed using the adapted Problem-Solving Adherence and Competence Scale (PST-PAC; **Appendix 14**).

Objective 3: Effectiveness Study (RCT)

Baseline demographic measures will be gender, age, education, marital status, employment status and clinical characteristics.

Primary outcomes: Diabetes distress will be assessed with the Problem Area in Diabetes (PAID) scale (46). Responses on the PAID will be summed and transformed to generate a scale score from 0-100, with ≥40 indicative of severe diabetes distress. The PAID scale has excellent reliability, validity and sensitivity to change.48, 49

Secondary outcomes: Depressive and anxiety symptoms (Kessler Psychological Distress Scale (K10)), emotional well-being (5-item World Health Organization Well-Being (WHO-5) Index),(53). Coping strategies will be assessed using the Coping Self-Efficacy Scale (CSES).(47)

The immediate effect (8 weeks) and sustained effect (6 months) of the intervention on diabetes distress, depressive and anxiety symptoms and secondary outcomes will also be evaluated.

Process outcomes. The Goal Attainment Scale will be used to evaluate the extent to which participants' individual goals are achieved. Quality-adjusted-life-years (QALYs) – important for Objective 4 – will be generated using the Assessment of Quality of Life 4 dimension (AQoL-4D),(48) a generic health-related quality instrument. We will also investigate the minimum number of sessions needed to achieve significant initial and sustained reductions in diabetes distress. These findings will inform the economic evaluation

Objective 4: Economic evaluation

A detailed costing will be undertaken using financial data and micro-costing methods. Within the trial, participants will be asked to complete a brief resource use questionnaire to collect information about other health care resources used and lost productivity. The AQoL-4D is a 12 item self-completed questionnaire that will also be collected. The scoring algorithm provides a total utility score on a scale from 0 to 1 based on Australian preferences for specific health states represented within the response items. The utility values at each time point are then used to calculate quality-adjusted-life-years (QALYs) using the area under the curve method.

Objective 5: Barriers and enablers to reach and implementation

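### External mental-health links and GP advice for screen failures depend on severe diabetes distress, so people excluded with PHQ-4 of 6 or more and PAID below 40 are promised neither

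*Protocol*

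**What the plan says.** The eligibility criteria in Protocol Section 7.2 require PHQ-4 below 6, for trial participants and training cases alike. The reason given carries no condition on PAID: "a score greater than or equal to 6 indicates moderate-severe symptoms and warrants further assessment and follow-up".

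Table 1, introduced in the same section as the pathways to be applied, has one row with a raised PHQ-4. It is the PAID >75 row, described as "Severe diabetes distress plus at least moderate depressive or anxiety symptoms". Only that row carries footnote b: "Provided with resources / referral to MH services and/or a referral to their GP". The row for PAID 25-75 exists only for PHQ-4 below 6 and is labelled "Moderate-to-severe diabetes distress but no/mild general symptoms".

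Section 6.1 (Objective 3, consent and screening) gives every ineligible person links to the NDSS emotional-health factsheets. It reserves external mental-health links and the recommendation to see a primary-care provider for a narrower group: "Those not eligible for the project because of indications of 'severe diabetes-distress and moderate-severe symptoms of depression or anxiety' (see Section 7.2"). Contact details for the research team are "provided on the Qualtrics form should the individual wish to discuss support available".

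Section 7.4 (effectiveness trial) repeats the condition. The additional support goes to "those not eligible for the project because of indications of 'severe diabetes distress and moderate-severe symptoms of depression or anxiety". It describes the factsheets that everyone receives as including resources for support. For ineligible training-case volunteers, Section 7.4 says only that they will be thanked.

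Section 13.1 defines severity on the PAID scale, "with ≥40 indicative of severe diabetes distress". Table 1 uses the plain word severe only above 75.

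**The concern.** The protocol states that one scale, the PHQ-4, calls for follow-up. It then makes the follow-up depend on a different scale, the PAID. Someone excluded because of raised depressive or anxiety symptoms, but with modest diabetes distress, meets the first statement and misses the second.

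The contrast with other groups is awkward. Control participants, who have PHQ-4 below 6 by design, are promised external mental-health links and, if needed, a GP referral (Section 6.1, Control). People who withdraw are offered the links and the GP recommendation (Section 9.3). People screened out with more symptoms but PAID below 40 are promised neither.

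Eligibility is decided automatically from the screening answers, so a form built literally to this text would reproduce the gap. What is at stake is the care of people who are screened out. The treatment comparison is not at stake.

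**Working it through.** No sample-size or power figure is involved, so the check sets the rules side by side for each PAID band, with PHQ-4 at 6 or more.

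Inputs:
- PHQ-4 cut of 6, and the Table 1 bands <25, 25-75 and >75: Section 7.2.
- Condition for external links and GP advice, namely severe diabetes distress and moderate-severe symptoms: Sections 6.1 and 7.4.
- Two candidate meanings of severe: PAID ≥40 (Section 13.1) and PAID >75 (the plain label in Table 1).

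| PAID, with PHQ-4 ≥6 | Eligible? | Table 1 row | External links and GP advice if severe is ≥40 | If severe is >75 |
|---|---|---|---|---|
| Below 25 | No | None | No | No |
| 25 to below 40 | No | None | No | No |
| 40 to 75 | No | None | Yes | No |
| Above 75 | No | Yes, footnote b | Yes | Yes |

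Three results follow.

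1. Below 40, neither meaning of severe is reached, so the joint condition fails on both readings. Only the factsheet links remain, and possibly the research-team contact. The contact sentence follows directly after the joint-condition sentence, so it is unclear whether it applies to all ineligible people. In any case, the individual has to make the approach.

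2. From 40 to 75, the answer turns on the definition. Under Section 13.1 the text covers these people. Sections 6.1 and 7.4 both refer the reader to Section 7.2 for the group, however, and the only raised-PHQ-4 row there is PAID >75. The text can be read as covering them, but the table does not show it.

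3. Above 75, the text covers everyone on both readings. The table prints PHQ-4 >6, which would leave out a score of exactly 6. An underline may have been lost when the PDF was read, and nothing here depends on it.

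Table 1 therefore has a raised-PHQ-4 row for 1 of its 3 PAID bands.

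**The case against.** The strongest reply is that nobody leaves with nothing. Every ineligible person gets links to factsheets that include resources for support. That stands, and it limits the point to the external-service links and the GP recommendation. The protocol does offer those two in addition to the factsheets, so it does not treat the factsheets alone as its answer to raised symptoms.

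Second, the COVID-19 checklist at the front of the protocol ticks a support statement at the end of survey instruments, as applicable, and a prompt review of data for disclosures of distress. A statement shown to everyone would need no PHQ-4 trigger and would narrow the gap. But both ticks sit under a question answered No, and the visible text does not say whether the screening form carries the statement. This counts against high confidence. It does not cure the wording.

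Third, the two uses of severe can be reconciled. If 25 to below 40 is moderate and 40 to 75 is severe, the Table 1 label for 25-75 is consistent with Section 13.1. That is plausible, and it leaves PAID below 40 as the firm part of the gap.

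A reader might also infer more than the documents support:
- That the live form withholds support. Appendix 9 is not shown, so this cannot be said.
- That the uncovered 0 to 40 stretch of a 0-100 scale means 40% of excluded people. Scale points are not people, and no screening counts are given.
- That the 198 people in the Section 11.4 follow-up count were exposed. They are enrolled participants. They show that recruitment is under way and nothing about screen failures.

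**Conclusion.** The point holds for the visible protocol text. People excluded with PHQ-4 of 6 or more and PAID below 40 are promised neither external mental-health links nor GP advice, although Section 7.2 says their score needs follow-up. For PAID 40 to 75 the text gives cover if severe means 40 or more, and only the Table 1 row is missing.

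The number of people affected is unknown. The conclusion assumes that the unseen screening form follows the protocol text and that no removed or unshown page sets a trigger on PHQ-4 alone. Severity is minor to moderate, and confidence is moderate. The trial result, eligibility and sample size are unaffected.

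**What to change.** - In Section 6.1 (consent and screening) and Section 7.4 (effectiveness trial), replace the joint trigger with: PHQ-4 score of 6 or more, whatever the PAID score.
- In Table 1, add rows for PHQ-4 ≥6 with PAID <25 and with PAID 25-75, both not eligible with footnote b. Make the last row ≥6 if the source does not already print it so.
- In Section 7.4, apply the same rule to ineligible training-case volunteers.
- Check that the display logic of the live screening form follows this rule.

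The cost is two table rows, possibly one symbol, a reworded or added sentence in three places and a check of the survey. Nothing changes in eligibility, sample size or analysis.
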